## Cognitive Stimulation Therapy for Residents With Dementia in Long-Term Facilities: A Quasi-Experimental Study Protocol

Dementia is a widespread disease among aging individuals, with reports addressing that approximately 5.8 million adults, ages 65 and older, in the United States have some form of the condition (Zubatsky et al., 2023). The Centers for Disease Control and Prevention (CDC) projects that by 2060, rates of this disease will rise to 14 million people (Centers for Disease Control and Prevention, 2019). Dementia is a prevalent developmental and progressive brain disease, involving the decline of memory, language, learning, judgment, problem-solving, visual-spatial skills, and attention (Kearney & Trull, 2018). The term 'dementia' encompasses various forms, with Alzheimer's disease being the most prevalent, accounting for 60%–78% of cases, and vascular dementia following at 15% (Kearney & Trull, 2018). As dementia progresses, it is typically classified into mild, moderate, or severe stages. The stages are indicative of the impairment of cognition; thus, mild dementia means mild cognitive decline and may indicate a decrease in independence (Dementia Care Central, 2023). For people with dementia (PwD), various symptoms can hinder the successful and safe completion of activities of daily living (ADLs). Management of dementia may include pharmaceuticals, Cognitive Behavioral Therapy, psychotherapy, and psycho-educational interventions, Behavioral Management Therapy, environmental approaches/modification, dementia support groups, memory training, alternative therapies, and cognitive stimulating environments (Alzheimer's Association, n.d.; Berg-Weger & Stewart, 2017).

### **Cognitive Stimulation Therapy**

Among non-pharmacological interventions, Cognitive Stimulation Therapy (CST) has emerged as a promising approach to support cognitive functioning and promote occupational

engagement in individuals with mild to moderate dementia. CST is a type of holistic evidence-based individual or group intervention program designed to stimulate learning, functionality, cognition, and quality of life (QoL) in mild-to-moderate dementia (Berg-Weger & Stewart, 2017; Bertrand et al., 2023; Orrell & Zarit, 2018). Research addresses that applying CST to the aging population can delay cognitive decline and can reduce the risk of dementia (Apóstolo et al., 2014; Berg-Weger & Stewart, 2017; Bertrand et al., 2023; Bhowmik et al., 2023; Yuill & Hollis, 2011). CST consists of structured group activities such as word games, hand movements, or making photo frames performed twice weekly for 7-weeks (Elmiyanti & Salamung, 2022). The general structure of each session includes an introduction, theme song, current affairs activity, the main activity, suggested activities for home, and closure (Berg-Weger & Stewart, 2017; Orrell & Zarit, 2018). CST is intended to stimulate thinking, concentration, and memory skills in PwD (Kelly et al., 2017; Woods et al., 2012, as cited in Saragih et al., 2022). Activities are implemented based on the interests and abilities within the group, and trained CST facilitators are skilled to adjust the activities in real time based on participation and engagement levels (Collins et al., 2023).

#### **Occupational Therapy and CST**

Occupational therapy helps people of all ages participate in meaningful daily activities—such as self-care, work, school, and community life—by using everyday tasks (occupations) to promote health, well-being, and independence (AOTA, 2025). Occupational therapy's scope of practice includes interventions for cognition, caregiver training, functional tasks, and group treatments (AOTA, 2020). Because CST incorporates interventions that resemble occupational therapy such as ADLs, instrumental activities of daily living (IADLs), leisure, health management, and social participation, it falls within occupational therapy's scope

of practice (AOTA, 2020). Occupational therapists possess specialized training that equips them for supporting PwD and facilitating the implementation of CST. With their therapeutic expertise, holistic approach, and client-centered focus, occupational therapists are equipped to deliver CST, especially in group settings, where they can manage group dynamics, address group and individual needs, prioritize client-centered care, and provide encouragement (Spector et al., 2008, as cited in Collins et al., 2023).

#### **Expanding CST: The Need for Occupational Therapy Involvement**

Research addresses the benefit of using CST with PwD in various settings such as outpatient, residential communities, inpatient, and virtual, but majority of these studies do not include occupational therapists administering CST (Aguirre et al., 2013; Apóstolo et al., 2014; Bertrand et al., 2023; Bhowmik et al., 2023; Cove et al., 2014; Gibbor et al., 2021; Gil et al., 2022; Lok et al., 2020; Orfanos et al., 2021; Zubatsky et al., 2023). International studies support the combination of occupational therapy and CST for the treatment of mild-to-moderate dementia (Collins et al., 2023; Yuill & Hollis, 2011). However, there is limited research on the efficacy of CST in the United States. According to University College London (2023), there are two U.S. contacts registered with the International CST Center who have administered CST in research studies. Currently, the St. Louis University and Perry County Memorial Hospital within St. Louis, Missouri are administering CST and hosting CST training sessions for professionals in the United States. Even though Perry County Memorial Hospital does provide CST as an occupational therapy service, research has not been implemented beyond Missouri nor includes outcome measurements in the long-term care setting.

Research in memory care aims to enhance care, cognition, independence, and QoL for PwD. The efficacy of CST in enhancing cognition in people with mild-to-moderate dementia has

been established (Woods et al., 2012, as cited in Orrell & Zarit, 2018). The cognitive and social stimulation provided during CST promotes occupational engagement and improvement in ADLs (Ryan & Brady, 2023). As dementia progresses, PwD often experience functional decline which can impact their ability to perform their ADLs (Chen, 2022). CST is an intervention that can help improve an individual's ability to perform and engage in their meaningful occupations. As healthcare and knowledge of dementia evolves, it is important to assess the effectiveness of CST and evaluate the qualifications needed to administer it within settings.

#### **Study Summary and Objectives**

This research examined the effectiveness of CST while aiming to support and validate the role of occupational therapy and promote its integration into long-term care settings across the United States. Currently, there is limited research on occupational therapists implementing CST with older adults living with dementia in long-term care facilities. The purpose and aims of this research study were to: 1) investigate the preliminary effect of CST on cognition and engagement in individuals with mild-to-moderate dementia, and 2) assess the feasibility of implementing CST in LTC facilities in the Cincinnati metropolitan area. The objective of this research was to answer the following question: Does CST improve cognitive functioning and increase engagement levels in individuals with mild-to-moderate dementia residing in long-term care facilities? We hypothesized that individuals with mild-to-moderate dementia who participated in a 7-week CST program in a long-term care facility would exhibit significantly higher levels of engagement and cognitive functioning compared to baseline.

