#### Methods

A quasi-experimental, single-group pretest-posttest design was used to evaluate the effects of engagement and cognitive functioning in a group CST program. The study was

conducted as a student-led research project by occupational therapy doctoral students from Northern Kentucky University (NKU) who had completed their didactic coursework, including a group intervention course, and their first Level II fieldwork prior to engaging in on-site activities.

Although a randomized controlled trial (RCT) was initially planned, recruitment challenges, time constraints, and logistical limitations led to a modification of the study design. The modification addressed an ethical concern regarding the control group not receiving the intervention, as a delayed intervention was not logistically feasible for the researchers. Due to the nature of the study design, no blinding of participants or researchers occurred. The study was approved by NKU's Institutional Review Board for human subjects research (IRB # 2562) and revisions to the study protocol were approved prior to the start of the intervention. The study was registered at ClinicalTrials.gov (NCT06978972) and made public in June 2025. The study was conducted from May to August 2025 at a long-term care facility in southeast Indiana that provides memory care, assisted living (ALF), and skilled nursing (SNF) care. Data was collected between June and August 2025.

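### The study question and the word effectiveness are causal, but one unblinded group tested before and after can show only change from baseline, and no section limits attribution to CST

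*Combined protocol and SAP*

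**What the plan says.** The Study Summary and Objectives section pitches its inference at three levels.

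- **Purpose and question, causal.** "This research examined the effectiveness of CST while aiming to support and validate the role of occupational therapy", and the objective is put as a question: "Does CST improve cognitive functioning and increase engagement levels in individuals with mild-to-moderate dementia".
- **Aim 1, partly hedged.** The aim is to "investigate the preliminary effect of CST on cognition and engagement in individuals with mild-to-moderate dementia". Aim 2 concerns feasibility.
- **Hypothesis, not causal.** Participants in a 7-week CST programme "would exhibit significantly higher levels of engagement and cognitive functioning compared to baseline".

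The Methods give the design: "A quasi-experimental, single-group pretest-posttest design was used to evaluate the effects". They explain that a randomised trial had been planned and was given up, and state that "no blinding of participants or researchers occurred". Study Procedures has a student other than the screener do the pre-tests and post-tests, with the intention of reducing bias.

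The Statistical Analysis Plan specifies a one-tailed Wilcoxon signed-rank test of pre against post, at .05 for the MoCA and at a Bonferroni level of .0045 for the OME-Modified, in participants who met a 50% attendance rule. No section says that change cannot be attributed to CST, names other explanations for change, or says how a significant result will be worded.

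**The concern.** The question is whether CST causes improvement. The analysis tests whether scores moved. These are the same only if scores would have stayed put without CST, and a single-group design offers no way to check that.

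The document itself describes features that could move scores without any CST effect:

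- The MoCA is repeated after 7 weeks, and no alternate form is mentioned.
- The tester is not described as blinded and necessarily knows which test is the post-test.
- On the OME-Modified, retesting with a different stimulus is described only at post-test and only for participants who showed little interest. If the retest score is the one used, change is pushed upwards.
- Dementia is described as progressive, which would push scores down.

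What is at stake is the conclusion. The stated significance levels limit chance findings of *change*; they set no limit on wrongly crediting that change to CST. A reader who takes the study question at face value would over-read a positive test, or under-read a null one.

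**Working it through.** **1. What the test addresses.** Write a participant's change as D = c + s + e, where c is the CST effect, s is any systematic shift from other causes, and e is random variation, symmetric about zero. The signed-rank test has the null hypothesis c + s = 0. The study question concerns c. With a concurrent control, s could be estimated and removed; with one group, only the sum c + s is observed.

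**2. The plan's own figures.** The only derived level is .0045 for the OME-Modified. 0.05/11 = 0.004545, so it reproduces if there are 11 comparisons; 0.05/10 = 0.005 and 0.05/12 = 0.0042 do not match. The number of comparisons is not stated. N = 10 comes from the recommended group size in the CST manual; no effect size, SD or power is given.

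**3. Illustration with c = 0.** Inputs from the document: n = 10, one-tailed test, levels .05 and .0045. Inputs assumed, because the document gives neither: the shift s and the SD of change. Changes are drawn from a normal distribution and rounded to whole points. The test is the exact signed-rank test with ties and with zeros dropped, using 20,000 simulated studies per setting. Entries are the share of studies declared significant.

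| n | Level | Shift s | SD 2 | SD 3 | SD 4 |
|---|---|---|---|---|---|
| 10 | .05 (MoCA) | 0 | 4% | 4% | 4% |
| 10 | .05 | +1 | 37% | 22% | 16% |
| 10 | .05 | −0.5 | 1% | 1% | 2% |
| 10 | .05 | −1 | <1% | <1% | <1% |
| 6 | .05 | +1 | 15% | 11% | 9% |
| 10 | .0045 (one OME-Modified comparison) | +1 | 5% | 2–3% | 2% |

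Independent repeats agree to within about a point. The n = 6 row is there because the SAP removes participants below 50% attendance, so the analysed number may be under 10. The SAP does not say whether p-values are exact; a normal approximation rejects more often, most visibly at n = 6.

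**4. The OME-Modified row.** The document does not give that scale's score range, so read the row as a shift of 1/2, 1/3 or 1/4 of an SD. The figures are per comparison; the chance that at least one of several comparisons crosses the threshold is higher and depends on correlations that are not given. With 7 or fewer participants, the smallest exact one-tailed p is 1/2⁷ = 0.0078, so .0045 cannot be reached.

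**5. Drift the other way.** If c = +1 and s = −1, then c + s = 0 and the test is positive in only about 4% of studies (first row). A real benefit would go unseen. The result cannot be attributed in either direction.

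**The case against.** The strongest reply is that the document is more careful than its study question. Aim 1 speaks of a preliminary effect, the other aim is feasibility, the hypothesis is limited to a comparison with baseline, and the Methods openly disclose the single group and the absence of blinding. The lack of attribution is a property of every such design. This largely stands: the hypothesis needs no change, and the mismatch is confined to the question and the effectiveness wording. But disclosing a design is not the same as limiting the conclusion, and the softer sentences do not override the stated question.

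Several stronger readings are tempting, and the document does not support them:

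- *That the plan commits to reading p ≤ .05 as proof that CST improves cognition.* No section states how a significant result will be worded. The over-reading is a risk left open, not a planned rule.
- *That causal wording was carried over from the abandoned randomised trial.* The superseded protocol is not available, so this cannot be shown.
- *That the MoCA rates apply to engagement.* The OME-Modified is held to .0045, where the rates are far lower.
- *That the bias must favour CST.* Decline from dementia would work against it.
- *That the SAP tests the value of occupational therapy delivery.* The phrase "aiming to support and validate the role of occupational therapy" is neither a numbered aim nor tied to any test. What can be said is that no other type of delivery is compared, so the outcome tests cannot support it.

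The Methods sentence about evaluating effects is also weak evidence of a causal claim: it goes on to refer to effects of engagement and cognitive functioning, and its meaning is unclear.

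**Conclusion.** The point holds as a mismatch of wording and inference. The question asked, and the stated examination of effectiveness, cannot be answered by an unblinded single-group before-after comparison; the hypothesis in the same section can. No section reconciles the two or limits attribution.

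The size is illustrative. For the MoCA at n = 10 and no CST effect, an assumed non-CST gain of 1 point raises the chance of a significant result from about 4% to between 16% and 37% (9% to 15% at n = 6). An assumed drift of −0.5 to −1 point lowers it to about 2% or less. For a single OME-Modified comparison, the corresponding upward shift gives about 2% to 5%. All of this rests on assumed shifts and SDs, normally distributed changes and exact p-values. The argument about attribution rests on none of them. The design, the test and the hypothesis are not themselves in error.

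**What to change.** Keep the design, the test and the hypothesis. Change the wording as follows.

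1. Reword the study question: *Do MoCA and OME-Modified scores change from baseline over a 7-week CST programme?*
2. In the purpose statement, replace *effectiveness* with *within-group change*.
3. Add to the SAP: *A significant result will be reported as preliminary change from baseline, not as an effect of CST. Without a control group, change may reflect retesting, attention, tester expectation, the course of the disease or other influences, in either direction.*
4. Add that the outcome tests will not be used as evidence validating occupational therapy delivery, which has no comparator in this study.

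Data collection ran from June to August 2025, so wording is what can still be changed. No new data or participants are needed. The cost is a less favourable headline claim.

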#### Methods

A quasi-experimental, single-group pretest-posttest design was used to evaluate the effects of engagement and cognitive functioning in a group CST program. The study was

conducted as a student-led research project by occupational therapy doctoral students from Northern Kentucky University (NKU) who had completed their didactic coursework, including a group intervention course, and their first Level II fieldwork prior to engaging in on-site activities.

Although a randomized controlled trial (RCT) was initially planned, recruitment challenges, time constraints, and logistical limitations led to a modification of the study design. The modification addressed an ethical concern regarding the control group not receiving the intervention, as a delayed intervention was not logistically feasible for the researchers. Due to the nature of the study design, no blinding of participants or researchers occurred. The study was approved by NKU's Institutional Review Board for human subjects research (IRB # 2562) and revisions to the study protocol were approved prior to the start of the intervention. The study was registered at ClinicalTrials.gov (NCT06978972) and made public in June 2025. The study was conducted from May to August 2025 at a long-term care facility in southeast Indiana that provides memory care, assisted living (ALF), and skilled nursing (SNF) care. Data was collected between June and August 2025.

#### **Participants**

Recruitment, data collection, consenting, and CST-related activities took place at Ridgewood Health Campus, including–Legacy Lane (memory care), the assisted living facility, and the health campus building, all located on the same site in Lawrenceburg, Indiana– using a convenience sampling approach. This is a facility owned and operated by Trilogy Health Services, LLC in Lawrenceburg, Indiana. Ridgewood Health Campus has facilities dedicated to memory care, skilled nursing, and assisted living. All facilities provide residents with apartments, 24/7 on-site healthcare staff, dining halls, transportation services, salons, indoor and outdoor common areas, and community gardens. Cognitive stimulation activities were held in the

memory care building (Legacy Lane) on the Ridgewood Health Campus. The memory care building includes open and accessible common areas that provide adequate space for conducting CST sessions without interfering with other facility operations. On-site nursing and medical staff were available as needed to support participant care. Researchers collaborated closely with facility staff to address any concerns related to the intervention, environment, or individual participants, ensuring the safety and well-being of everyone involved. In the event of an adverse incident during the study or treatment, researchers planned to follow HIPAA regulations and the facility's established protocols. Incidents were planned to be promptly reported to the Principal Investigator (PI) and the facility staff.

An occupational therapy student researcher collaborated with staff on-site during the spring of 2025 to review the study information to prepare the staff to identify individuals who meet the inclusion criteria. The student performed recruitment, which involved convenience sampling within the SNF, ALF, and memory care units, contacting the participant and, when applicable, their power of attorney (POA) using approved recruitment scripts, information handouts, and consent forms, in person or by phone. The informed consent forms and participant handout were developed at an 8th-grade reading level to ensure accessibility and understanding for individuals with cognitive impairments or limited health literacy. The POA is an individual who is legally responsible for an individual and was able to provide consent for the study alongside their family member with dementia. Two consent processes were used: a dual consent form for individuals with a POA, requiring signatures from both parties in recognition of the cognitive considerations associated with dementia, and a standard form for those without a POA. Consent was obtained either electronically or in person with physical signatures. All participants and their POAs (if applicable) provided written or verbal reconsent prior to the intervention due

to the study design change. The student repeated this process with multiple participants and POAs until the sample size was achieved. Before recruitment, researchers established a target sample size based on the *CST Making a Difference 1* Manual, which recommends 5 to 8 participants per group. To account for potential variability in attendance due to scheduling conflicts, mood fluctuations, or health-related absences, a sample size of 10 participants (N = 10) was set to help maintain a consistent group size of 5 to 8 participants per session.

Characteristics of individuals enrolled in the intervention group included individuals who were: 18 years or older with diagnosed mild-to-moderate dementia according to The Diagnostic and Statistical Manual of Mental Disorders, Fifth Edition (DSM-5), confirmed by medical records, or a score in the mid-range (18–55) on the Alzheimer's Disease Assessment Scale-Cognitive Subscale (ADAS-Cog), live in a long-term care facility, and were engaging in at least 45 minutes a week of recreational or social activities. Additional characteristics included proficiency in English, adequate vision, hearing, and speech to participate in groups. All participants and their POAs (if applicable) who provided consent were included.

Characteristics of individuals that were to be excluded from the study were: 17 years of age or younger; were not receiving maintenance or recreational services; have communication barriers such as aphasia; do not speak English as a first or second language; have a severe case of dementia; receiving hospice care; score in the high range (56–70) or no impairment range (0–17) on the ADAS-Cog; prior CST treatment; history of traumatic brain injury or learning disability; and participation in a concurrent clinical trial that could influence outcomes that are being assessed.

